### 5-Patient selection

#### 5.1. Inclusion criteria

- Histologically proven non-lobular invasive breast recurrence (IBR)
- Time from whole breast radiation following the initial lumpectomy >5 years
- Unifocal tumor
- Recurrent tumor size  $\leq$  2 cm
- Adequate breast size for a second breast-conserving surgery with acceptable cosmetic result
- Bilateral breast mammogram within 90 days prior to study entry
- Breast MRI within 90 days prior to study entry
- Histological grade I-II
- Estrogen-receptor-positive tumor (ER+)
- Cerb2-negative tumor
- N0 status (ultrasound of the axillary area is required, with fine needle aspiration cytology, in case of doubt)
- M0 status determined by PET-CT or both thoraco-abdominal CT and bone scan within 90 days prior to study entry
- Prior radiotherapy delivered within a standard fractionation schedule
- Performance status (ECOG) 0-1
- Women  $\geq$  50 years
- Absence of any psychological, familial, sociological, or geographical conditions with a potential to hamper compliance with the study and follow-up schedule
- Affiliated to the French Health Insurance regimen
- Written and signed informed consent form.

## 5.2. Exclusion criteria

- Disease previous non-invasive breast carcinoma (in situ)
- Disease previous contralateral breast cancer
- Multifocal and/or multicenter recurrence
- Lobular carcinoma
- Estrogen-receptor-negative tumor (ER-)
- Cerb2 (her2) overexpressed - breast cancer
- Extensive intraductal component (EIC) on biopsy
- Lymph vessel invasion on biopsy
- N1-3 status: Regional cytological or histologically proven node recurrence
- M1 status: Metastatic disease
- cT4 (Skin or muscle involvement) or Paget's disease of the nipple
- Prior radiotherapy delivered within an accelerated or hypo-fraction schedule
- Prior malignancy other than non-melanoma skin cancer unless the patient has been disease free for at least 5 years
- Patients with a small breast volume, technically unsatisfactory for a second conservative surgery or intraoperative breast irradiation.
- Preoperative chemotherapy or hormone therapy for local relapse
- Connective tissue disease or scleroderma, contraindicating radiotherapy
- Age < 50 years
- Known BRCA1/2 gene mutation (genetic testing is not required)
- Failure to comply with medical monitoring test for geographical, social or psychological reasons

## 6-Methodology and study design

We propose a prospective, multicenter, single arm Phase II design to evaluate the feasibility of repeated breast-conserving surgery combined with re-irradiation using IORT after local recurrence of breast carcinoma.

### **The study is planned to enroll 65 patients.**

The patient must provide a signed informed consent form prior to any study related procedure. The principal measured outcome will be the cutaneous fibrosis rate 12 months after treatment. We considered that a rate of 20% or more of Grade  $\geq 2$  fibrosis would be unacceptable.

All patients will be followed for:

- Survival and local breast control after this study treatment for an extended carcinologic follow-up.

- Toxicities during and after treatment (3, 6, 12 and 24 months after IORT and each year during 3 years)
- Survival follow-up will be done every 3, 6, 12 and 24 months after IORT and each year during 5 years by clinical visits unless death lost to follow-up or withdrawal of consent.

The survival follow-up period will continue for 3 years after the last patient was included in the study.

The end of study (last patient last visit) will occur after all patients have completed their last assessment.

### **Temporary interruption and definitive termination of the study**

The study could be suspended or stopped by the sponsor after meeting with the principal investigator or under the request of the competent authority and/or the Committee for the Protection of Patients (CPP) for a high fibrosis rate

## **7-Treatment**

---

### **7.1. Second breast surgery**

The surgery is performed following a classic or ambulatory hospitalization scheme, according to the equipment and habits of the team.

#### **7.1.1. Axillary management**

For the patients with previous axillary surgery, there is no consensus about the management of the axilla. If the initial surgery has disrupted the lymphatic vessels draining, the lymphatic mapping with sentinel node is considered to be unsuitable.

For the node negative patients assessed by clinical and ultrasound examination, the surgical procedure will be adapted to the initial management:

- No axillary surgery will be performed after a previous standard axillary lymph node dissection
- Lymph node dissection can be discussed after an initial mapping with lymph node procedure.

Axillary node involvement, when preoperatively or intra-operatively proved, is a total contraindication for entering this trial.

## 7.1.2. Lumpectomy

Lumpectomy is performed with an incision, left to the surgeon's choice for a broad glandular resection, from deep dermis to face pectoral. Orientation of the specimen is then required.

The intraoperative evaluation of the margins will be realized according to the habits of the team, to ensure margins are free from tumor (through pathological frozen section when achievable). A safe margin is required to ensure the complete resection of the tumor.

Safe margins are defined as « no ink on tumors », as recommended on the New 2014 Guidelines on the Society of Surgical Oncology and the American Society for Radiation Oncology (38).

Then, the cavity is prepared to receive the INTRABEAM™ system, to make the gland stick around the collimator and the size of the Intrabeam™ radiation probe applicator will be chosen to fill the tumorectomy cavity.

## 7.2. Radiotherapy by IORT for re-irradiation

### 7.2.1. Equipment and physics

The IntraBeam™ device is a mobile light machine (1.6 kg) with a miniature system providing a source of 50-kV x-rays at the tip of a 3 mm diameter tube placed at the center of a spherical applicator. Accelerated electrons, aimed on a gold target, produce a spherical radiation field, with an isotropic dose-distribution around the tip of the probe.

These low energy X-rays are characterized by a sharper dose fall-off to the tissue depth than electrons or high-energy-photons. Spherical applicators are fixed at the end of the source and range in size from 2.5 to 5cm.

The X-ray source is combined with a small control consol. The operating room requires a simple shielding and, according to our national recommendations from the Authority for Nuclear Safety (ASN), a mandatory visit for official approval before any treatment. For radiation protection reasons, IORT is realized without any medical staff in the operative room.

Before each treatment, a medical physicist must control and validate the calibration of the processor (with PAICH: Probe Adjuster Ionization Chamber Holder and PDA: PhotoDiode Array), check the geometric alignment, the alignment of the electron beam in the "needle", the isotropy of the X-ray source, and the dose rate.

During treatment, the physicist programs the machine and waits for the end of treatment.

The nine French teams, involved in the National Cancer Institute network (INCa) and associated to this study, have obtained the required approvals and the experience of this specific technique.

The IORT treatment requires an optimal collaboration between the surgeon, the radiation oncologist and the medical physicist.

### **7.2.2. Modalities of IORT:**

Prior to the insertion of the adequate applicator in the surgical cavity, the surgeon cautiously checks the hemostasis, the perfect vicinity (absence of blood or serum) of the excision cavity. The presence of blood or serum would seriously reduce the dose received by the surrounding mammary gland in this situation of important steep dose fall-off.

The diameter of the applicator, varying from 25 to 50 mm, is chosen under visual control, by the surgeon and the radiation oncologist, in order to be perfectly adapted to the size of the cavity left by the removal of the tumor. Thanks to its spherical shape, the applicator is easily covered by the gland and does not require extensive tissue mobilization, which is a source of late fat necrosis.

The cavity tissue will then be approximated around the spherical applicator with one or two purse string sutures with a harmonious thickness of mammary gland

The suture is then tightened. Sterile gauzes or two Beckmann orthostatic spacers are added to obtain adequate skin spacing between the applicator and the skin, defined as  $\geq 1$  cm, to avoid skin toxicity.

The course of the irradiation is monitored by the radiation oncologist and the medical physicist. A unique dose of 20 Gy is prescribed at the applicator surface and the time of irradiation depends on its diameter with a median of about 30 minutes (ranging from 18 to 40 minutes). The exact length of the radiation time is determined by the applicator size (ranging from 20 to 40 minutes) and the additional time for the entire IORT procedure will be around 40 to 60 minutes. Then, the surgeon removes the applicator. Surgical clips are placed in the tumor bed to facilitate further imaging follow-up. The cavity is closed and remodelled. A post-operative drainage could be necessary.

## **7.3. Additional treatments**

Each case will be discussed during a multidisciplinary committee.

### **7.3.1. Local treatment**

In case of involved margins on the definitive pathology report, a new surgery is required. New conservative surgery or mastectomy will be proposed according to histological and clinical presentation.

No additional external irradiation will be delivered.

### 7.3.2. Systemic treatment

An adjuvant hormone treatment will be prescribed, based on tamoxifen or an aromatase inhibitor in postmenopausal women, excepted for women with contraindications.

Adjuvant chemotherapy has to be discussed in a dedicated multidisciplinary breast committee.

### 7.3.3. Further treatments:

In case of second local relapse, further management of the patient must be decided in a multidisciplinary breast committee.

## 8-Clinical evaluation and follow-up procedures

### 8.1. Inclusion

The following procedures and assessments will be performed prior to the IORT:

- The patient must provide a signed informed consent form prior to any study related procedures
- Eligibility criteria
- Demographics
- Physical examination: body weight, height, body mass index, clinical stage
- WHO performance status

  

- Diagnosis of isolated local recurrence:**

All patients with breast cancer recurrence receive standardized staging:

- Clinical Examination (palpation of the breast and axillary area)
- Mammography and ultrasonography of the breast (tumor size and topography).
- Breast magnetic resonance imaging to evaluate the size and unifocality of the recurrence.
- **Biopsy:** Histological verification is mandatory, reporting pathology grade, ER, PR, HER 2 status, and Ki 67.
- **Axillary area** assessment must be evaluated by physical examination and ultrasound, with a fine needle aspiration cytology in case of doubt (78,79).
- A PET-CT or a thoraco-abdominal CT and bone scan will be performed to detect any metastatic disease prior to study entry.

- Complete medical history, symptoms, and ongoing medications
- Menopausal status
- Quality of life questionnaires EORTC QLQ-C30/BR23
- Photography of the breast
- Blood sampling for Proteomic assay

## 8.2. IORT

- Effusion tumour bed sampling for Genomic assay (optional)

## 8.3. 15 days after IORT

- Physical examination: body weight, local and systemic related IORT toxicities
- WHO performance status
- Clinical Examination (palpation of the breast and axillary area)
- Clinical Breast skin cosmetic evaluation
- Photography (cosmetic evaluation)
- Quality of life questionnaires EORTC QLQ-C30/BR23

## 8.4. Follow up period (3, 6, 12, 24, 36, 48, 60 months)

- Physical examination: body weight, local and systemic related IORT toxicities
- WHO performance status
- Clinical Examination (palpation of the breast and axillary area)
- Mammography and ultrasonography of the breast at 12 months only 6 months and 1 fs/year
- Breast magnetic resonance imaging at 12 months (optional)
- Clinical cosmetic evaluation
- Photography (cosmetic evaluation) (until 60 months)
- Quality of life questionnaires EORTC QLQ-C30/BR23 (until 24 months)

## 9-Primary endpoint

The fibrosis grade will be scored following the NCI CTCAE scale v4.0 at 12 months after the IORT (73).

## 10- Secondary endpoints

Definitive cosmetic results:

- assessed by a physician

- Pictures will be taken before treatment, after 15 days, 3, 6, 12 and 24 1fs/year until.

Toxicities (excluding fibrosis):

- assessed by a physician
- Grade will be scored following the NCI CTCAE scale v4.0 at 15 days, 3, 6, 12 and 24, 36, 48 and 60 months after the IORT.

Quality of life:

- assessed by a patient
- EORTC QLQ-C30, QLQ-BR23 questionnaires delivered before treatment, and after 15 days, three, six and twelve and twenty-four months.

Local relapse-free survival (L-RFS):

- L-RFS is defined as the time from surgery with IORT to any ipsilateral breast tumor recurrence, or death, whichever occurs first.

Metastasis Relapse-free survival (M-RFS):

- M-RFS is defined as the time from the surgery with IORT to any metastatic disease (excluding the ipsilateral breast, contralateral breast, regional lymph nodes), or death, whichever occurs first.

Disease-free survival (DFS):

- DFS is defined as the time from the surgery with IORT to any recurrence, including local recurrence, metastasis, appearance of a second primary tumor, or death from any cause, whichever occurs first.

Overall survival (OS):

- OS is defined as the time from surgery with IORT to death from any cause.

Mastectomy-free interval:

- MFI is defined as the time from the surgery with IORT to a mastectomy for any reasons (all other events will be ignored). All patients without mastectomy will be censored at last follow-up.

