### 1.1. Introduction

Breast cancer is by far the most frequent cancer among women, with an estimated 1.38 million new cases diagnosed in 2008 (23% of all cancers in women). It is now the most common cancer for women, worldwide, both in developed and developing regions (1). In France, with 53 000 new cases diagnosed in 2011, breast cancer represents 33% of all feminine cancers (2).

Nowadays, thanks to perpetual progress in screening and early diagnosis, most of the cases can benefit from breast-conserving surgery and adjuvant radiation therapy, which is assessed in huge Phase III trials, to provide equivalent long-term survival (3,4).

The risk of ipsilateral breast tumor recurrence (IBTR) is influenced by different factors, such as age, family susceptibility, pathological characteristics and systemic adjuvant treatments. In 2013, this risk of IBTR after lumpectomy and radiation therapy is still about 10% and 15 % at 10 and 20 years, respectively (5).

Actually, IBTR is a relatively frequent clinical situation occurring sometimes years or decades after the initial breast-conserving treatment (BCT). Today, clinicians face the delicate issue of determining the optimal therapy modalities for these patients. After conservative treatment, local recurrence is defined by the occurrence of a tumor in the mammary gland previously operated and irradiated.

Beyond the generated psychological trauma (with discouragement and loss of confidence in treatments), this local relapse constitutes a turning point in the evolutionary history of these patients with an increased risk of distant progression.

The clinical presentation and histopathological prognosis of these local recurrences are very heterogeneous. In some situations, IBTR are considered as the foremost marker of aggressive cancer, where the metastatic risk represents the main issue. In other situations, IBTR (i.e. indolent and late ones) are considered as less pejorative events, for which the optimal loco-regional treatment must be identified.

Indeed, for these patients, a therapeutic de-escalation must be considered, based on a different approach, such as a second conserving surgery combined with partial breast irradiation. A traumatic and mutilating mastectomy could, therefore, be avoided in some extremely selected situations.

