### 1.3. Local recurrence and treatment

#### 1.3.1. SURGERY

##### *Standard salvage mastectomy*

Salvage mastectomy represents the current standard of care for IBTR. This radical treatment is supposed to be the gold-standard, as a second conservative surgery may lead to unacceptable cosmetic outcome and given the second local relapse rate resulting from a purported impossible re-irradiation of the breast.

Nevertheless, the risk of second relapse is not eliminated by mastectomy and remains quite high: several single institutional studies describe rates of chest-wall recurrence around 10%, range from 2 to 32%, (23,25,35,36), principally influenced by the delay between the first treatment and IBTR (8).

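### The recurrence component of L-RFS is confined to the ipsilateral breast, so as worded a chest-wall or scar recurrence after mastectomy counts in DFS but not in L-RFS

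*Protocol*

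**What the plan says.** The Synopsis (Assessment criteria) and section 10 word the endpoint identically: "L-RFS is defined as the time from surgery with IORT to any ipsilateral breast tumor recurrence, or death, whichever occurs first". Its events are therefore recurrence in the breast on the treated side, and death.

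Section 7.3.1 describes a route to mastectomy: "In case of involved margins on the definitive pathology report, a new surgery is required". It continues: "New conservative surgery or mastectomy will be proposed according to histological and clinical presentation". Section 10 also defines a mastectomy-free interval whose event is a mastectomy of any cause.

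On failure after mastectomy, section 1.3.1 (Standard salvage mastectomy) says that "the risk of second relapse is not eliminated by mastectomy and remains quite high", and that "several single institutional studies describe rates of chest-wall recurrence around 10%, range from 2 to 32" per cent.

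DFS in section 10 counts every recurrence. The M-RFS event is "any metastatic disease (excluding the ipsilateral breast, contralateral breast, regional lymph nodes), or death, whichever occurs first". The chest wall is not among the excluded sites.

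**The concern.** After a mastectomy with no earlier in-breast recurrence, only death can still be an L-RFS event. If the disease returns in the ipsilateral chest wall or scar, the patient has failed locally in the ordinary sense and has a DFS event, but the L-RFS definition does not register it. Involved margins are one stated reason for the mastectomy, so the patients affected may not be those at lowest risk of local failure.

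The classification is unsettled in a second place. The M-RFS exclusions leave out the chest wall, and section 1.2 says that skin or subcutaneous involvement is to be regarded as metastatic. One reader could classify the event as metastatic and another could count it in DFS alone.

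At stake is the meaning of a descriptive secondary endpoint that readers will take as the trial's measure of local control.

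**Working it through.** **The texts side by side**

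Consider a patient with involved margins who has a mastectomy and later an ipsilateral chest-wall recurrence.

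- MFI (section 10): event at the mastectomy.
- DFS (section 10): event at the recurrence, since any recurrence counts.
- L-RFS (Synopsis, section 10): no event at the recurrence, since it is not in the breast.
- M-RFS (section 10): unclear. The chest wall is not excluded, and section 1.2 points towards metastatic for skin or subcutaneous disease.

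**Does the Protocol regard this as local failure?** Section 1.3.1 does. It presents chest-wall recurrence as the second relapse that mastectomy does not eliminate. It also compares local recurrence after repeat lumpectomy and after mastectomy: 38% against 25% in the French and Dutch cohorts, and 19% and 33% against 4% and 12% in the Swedish and Italian cohorts. Those benchmarks include post-mastectomy failures; L-RFS as worded does not.

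**Direction.** For each patient, the time to an L-RFS event under the narrow wording is never shorter than under a wording that adds the chest wall. The omission can therefore only favour the treatment.

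**Size.** The Protocol states no figure to reproduce. The inputs are:

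- N = 65 planned patients (section 6).
- m = share having a mastectomy without earlier in-breast recurrence. The Protocol does not give it; 5%, 10% and 20% are assumed.
- c = chest-wall recurrence after salvage mastectomy: about 10%, range 2% to 32% (section 1.3.1, with no time horizon).

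Missed events = N × m × c. Effect on the L-RFS proportion in percentage points = 100 × m × c.

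| m | Patients (65 × m) | c = 2% | c = 10% | c = 32% |
|---|---|---|---|---|
| 5% | 3.25 | 0.07 events (0.1 points) | 0.33 (0.5) | 1.04 (1.6) |
| 10% | 6.5 | 0.13 (0.2) | 0.65 (1.0) | 2.08 (3.2) |
| 20% | 13 | 0.26 (0.4) | 1.30 (2.0) | 4.16 (6.4) |

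For example, 65 × 0.10 × 0.10 = 0.65 events, and 100 × 0.10 × 0.10 = 1.0 point.

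For scale, assume a true L-RFS proportion of 90% and no censoring. The 95% half-width with 65 patients is 1.96 × √(0.9 × 0.1 / 65) = 0.073, or about 7 points. At c = 10% the effect lies well inside that.

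**The case against.** The best defence has four parts.

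**The wording need not be read so narrowly.** The endpoint is called local relapse-free survival, and the background uses local for post-mastectomy failures. Section 1.1 does say that "local recurrence is defined by the occurrence of a tumor in the mammary gland previously operated and irradiated", but it limits this to the situation after conservative treatment. An investigator might therefore record a chest-wall recurrence as a local relapse. This shows that the classification depends on the reader. It does not remove the problem, because the operative definition names the breast in both places.

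**In-breast control is a legitimate target.** The trial asks about a second breast conservation, and after mastectomy the irradiated bed has been removed. That is a fair choice, but the endpoint's name and the benchmarks in section 1.3.1 suggest local control more broadly. If the narrow target is intended, the Protocol should say so.

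**Nothing is lost to the trial.** MFI records the mastectomy and DFS the recurrence. This stands, and it limits the importance of the point.

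**Handling of mastectomy can be left to the analysis plan.** Censoring rules can. The list of events, however, is already fixed here, and censoring at mastectomy would still not count the later failure.

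Three stronger readings are tempting but unsupported.

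- A reader might infer that L-RFS counts nothing but in-breast recurrence. Death is also an event, so a patient who dies after a chest-wall recurrence has an L-RFS event, only later.
- A reader might infer that the patient in the example is carried as locally controlled at 24 months and 3 years. The Protocol gives a censoring rule only for MFI and is silent for L-RFS, so this does not follow.
- A reader might put the loss at 7% to 13% of local failures. That takes 15% positive margins (section 1.3.3), assumes that half to all of these patients have a mastectomy, and sets 0.49 to 0.98 missed events against 65 × 0.10 = 6.5 expected relapses: 0.49 / 6.99 = 7% and 0.98 / 7.48 = 13%. The margin rate comes from a different, retrospective external-beam series, the mastectomy share has no source, and a chest-wall rate without a horizon is set against a 5-year figure.

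**Conclusion.** The point holds as a minor defect of definition. Read literally, L-RFS omits an ipsilateral chest-wall or scar recurrence after mastectomy, although DFS counts it and the Protocol's background regards it as relapse. Its M-RFS status is open. Any resulting error is one-sided, towards better apparent local control.

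The likely size is about one event or fewer in 65: 0.3 to 1.3 events, or 0.5 to 2 points, at a 10% chest-wall rate, and 0.1 to about 6 points over the quoted range. This rests on an assumed mastectomy share of 5% to 20% and on a recurrence rate with no stated time horizon, whereas section 14.3 reports L-RFS at 12 months, 24 months and 3 years. The figures illustrate scale; they do not estimate the bias.

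L-RFS is descriptive, with no threshold or decision attached. The fibrosis endpoint, the sample size and the stopping rule on cancer deaths are untouched.

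**What to change.** In the Synopsis and section 10, define the L-RFS event as tumour recurrence in the ipsilateral breast or, after mastectomy, in the ipsilateral chest wall or scar, or death. In the same two places, add the ipsilateral chest wall to the sites that do not count as metastatic disease for M-RFS, so that the remark in section 1.2 cannot be used to classify the event differently.

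The cost is one phrase in each definition, with no change to treatment, visits or sample size. DFS already requires every recurrence, and M-RFS already requires its site. The case report form is not shown, so it should be checked that chest wall and scar can be recorded as sites. The L-RFS estimate may become slightly less favourable, and pure in-breast recurrence would have to be described separately if it is wanted.

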### ***1.3.3. Second conservative surgery with additional radiotherapy***

Several teams attempted to reduce the high rate of local relapse by adding a second adjuvant radiotherapy. However, delivering a second new whole breast irradiation is delicate, as normal tissue tolerance does not permit a second full-dose course of irradiation in the whole mammary gland.

Due to the impossibility to re-irradiate the whole breast, radiotherapy has not been really evaluated in this situation, until the birth of the concept of partial breast irradiation (PBI). According to the high rate (20% at 5 years, ranging from 7 to 32%) of the second local relapse observed after a second conservative surgery (23–26), an additional re-irradiation with various PBI techniques (interstitial brachytherapy, 3D external radiotherapy or intra-operative irradiation) were expected to bring interesting results.

Partial Breast Irradiation (PBI) is an innovative approach: PBI reduces both duration and volume of irradiation to the portion of breast that is at higher risk for recurrence and also spares the surrounding previously irradiated critical organs.

The concept of PBI is based on the fact that the majority of the local relapses occur close to the tumor bed (42–44). PBI has been developed during the last decade in an adjuvant setting after BCS. For selected patients with good prognosis tumors, PBI offers non inferior local-relapse rates at 4 years (45). Based on current published evidence and experts' opinion, the American and European Societies for therapeutic radiation oncology (ASTRO and ESTRO, respectively) provided in 2009 a Consensus Statement for the use of accelerated PBI in adjuvant setting (46,47).

This evaluation of PBI in the situation of local relapse has been performed mainly through single institutional retrospective or prospective studies using various techniques such as brachytherapy (29,30,48,49), external 3D conformal RT (27), or intraoperative radiation therapy (IORT) (50). The promising results showed a 5-year second local relapse rate of 10% (27–29).

No Phase III randomized trial has yet evaluated the benefit of the second course of irradiation. Nevertheless, retrospective or prospective single institution studies report a lower rate of 5-year second local relapse (from 10% to 20%) (27–30).

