### 14.3. Statistical analysis

Statistical analyses will be detailed in the statistical analysis plan developed before the database is frozen.

Baseline characteristics, compliance to treatment, safety, and carcinologic events will be described.

Qualitative data will be described by frequencies and percentages and associated 95% confidence interval.

Continuous parameters will be described by mean, standard deviation, median and range.

The primary endpoint will be described by the percentage of patients without fibrosis at 12 months and its 95% confidence interval.

For secondary endpoints, EORTC QLQ-C30 and QLQ-BR23 will be described according to EORTC scoring manual at baseline and for each visit.

Time to event endpoints (L-RFS, M-RFS, DFS, OS and mastectomy-free interval) will be estimated using Kaplan-Meier method and described by their rates and 95% confidence intervals at 12 months, 24 months, and 3 years.

Statistical analyses will be performed with STATA software v13 (Stata Corporation, College Station, TX, USA).

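### Mastectomy-free interval censors deaths under Kaplan-Meier, which slightly overstates the probability of mastectomy

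*Protocol*

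**What the plan says.** Section 10 of the protocol (and the synopsis, in the same terms) runs mastectomy-free interval (MFI) from surgery with IORT "to a mastectomy for any reasons (all other events will be ignored", and then adds: "All patients without mastectomy will be censored at last follow-up". Death is one of the other events, so a patient who dies without a mastectomy is censored.

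Section 14.3 names the estimator: "Time to event endpoints (L-RFS, M-RFS, DFS, OS and mastectomy-free interval) will be estimated using Kaplan-Meier method". The results are to be "described by their rates and 95% confidence intervals at 12 months, 24 months, and 3 years".

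The endpoint, the censoring rule, the estimator and the time points are thus all fixed in the protocol.

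Local relapse-free survival (L-RFS) is built differently. It is the "time from surgery with IORT to any ipsilateral breast tumor recurrence, or death, whichever occurs first", so death counts as an event there.

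**The concern.** Kaplan-Meier assumes that a censored patient remains at risk and would have behaved like those still under observation. That is reasonable for a patient whose follow-up has simply ended. It is not reasonable for a patient who has died, because death rules out a later mastectomy. If deaths are censored, the weight of each dead patient passes to the survivors, and one minus Kaplan-Meier exceeds the proportion of women who actually have a mastectomy.

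Breast preservation is the stated motive for the second conservative operation (sections 1.1 and 1.3), so readers will take the reported MFI rate as the share of women who kept or lost the breast. As planned, it answers a different and hypothetical question: the risk of mastectomy if nobody could die. The direction of the error is against the treatment, since it makes mastectomy look somewhat more frequent than it is.

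**Working it through.** The protocol gives no expected MFI figure, so there is nothing to reproduce. The check sizes the bias.

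**Inputs**
- Mastectomy rate: the protocol gives none. Two assumptions are used: a hazard of 3% per year, and a net 5-year risk of 10% to 20%. The latter borrows the range that section 1.3.3 gives for second local relapse after partial re-irradiation.
- Mortality: an assumed 2% to 5% per year, and 5-year overall survival of 60% (section 1.2) and of 76% and 88% (section 1.3.2).
- Time points: 12 months, 24 months and 3 years (section 14.3).
- Number of patients: 65 (section 6).

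**Formulas** (constant hazards h for mastectomy and d for death, an assumption)
- One minus Kaplan-Meier with deaths censored: 1 − exp(−h·t)
- Cumulative incidence with death competing: h/(h+d) × [1 − exp(−(h+d)·t)]
- Conversion from 5-year figures: h = −ln(1 − risk)/5 and d = −ln(OS)/5

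**Mastectomy hazard 3% per year, at 3 years.** One minus Kaplan-Meier is 1 − exp(−0.09) = 8.61% in each case.
- d = 0.02: 0.03/0.05 × [1 − exp(−0.15)] = 8.36%. Excess 0.25 points.
- d = 0.05: 0.03/0.08 × [1 − exp(−0.24)] = 8.00%. Excess 0.6 points.
- OS 60%, so d = −ln(0.60)/5 = 0.1022: 0.03/0.1322 × [1 − exp(−0.3965)] = 7.43%. Excess 1.2 points.

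**Net 5-year mastectomy risk 10% or 20%, at 3 years**

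| Net 5-year risk | 5-year OS | 1 − KM | Cumulative incidence | Excess (points) |
|---|---|---|---|---|
| 10% | 88% | 6.13% | 5.90% | 0.23 |
| 10% | 76% | 6.13% | 5.65% | 0.47 |
| 10% | 60% | 6.13% | 5.29% | 0.84 |
| 20% | 88% | 12.53% | 12.07% | 0.46 |
| 20% | 76% | 12.53% | 11.57% | 0.96 |
| 20% | 60% | 12.53% | 10.83% | 1.70 |

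Over this grid the excess is 0.03 to 0.21 points at 12 months and 0.10 to 0.80 points at 24 months. It grows with time: at 5 years, which section 14.3 does not report, it would be 0.6 to 4.2 points.

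**Against precision.** With 65 patients and no loss to follow-up, the 95% half-width is about 1.96 × √[p(1−p)/65]. That gives 5.8 points at p = 6.13%, 6.8 points at 8.61% and 8.0 points at 12.53%. The 0.25 to 0.6 point excess is thus less than a tenth of the half-width (0.6/6.8 = 0.09). The largest value in the table is about a fifth of it (1.70/8.0 = 0.21).

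**The case against.** **The bias is immaterial.** The excess is well inside the confidence interval at every planned time point, no decision hangs on MFI, the definition says openly that other events are ignored, and overall survival is reported beside it. This stands as an argument about weight. It does not make the estimator right for the quantity a reader will take from it.

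**The inputs may overstate the bias.** The 60% survival figure describes local relapses in general, of which section 1.2 says 5% to 10% already have synchronous metastases. This trial requires N0, M0, ER-positive, grade I-II tumors of at most 2 cm, more than 5 years after radiotherapy. The 76% and 88% come from a chemotherapy trial that also enrolled ER-negative relapses. Section 7.3.1 allows mastectomy for involved margins on final pathology; such events fall early, before deaths can compete, so constant hazards probably overstate the error. This stands as well, and the lower end of the range is the more plausible.

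**A stronger reading is tempting for L-RFS.** A reader might infer that L-RFS is also wrong because it mixes death with relapse, and that second local relapse is therefore not estimated at all. The protocol does not support this. L-RFS is a properly defined relapse-or-death composite, and Kaplan-Meier is valid for it. Section 14.3 says that carcinologic events will be described, with percentages and 95% confidence intervals for qualitative data, so a proportion with second local relapse falls within the plan. Nowhere does the protocol plan to set L-RFS against the relapse rates in its rationale, and it does not say by what method those published rates were obtained.

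What remains is a caution about interpretation: L-RFS is not a local relapse rate. With a 10% net 5-year relapse risk and 88% 5-year survival, the same formulas give a 3-year relapse-or-death probability of 13.1% against a relapse probability of 5.9%.

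**Conclusion.** The point holds for MFI. The protocol's own censoring rule, combined with Kaplan-Meier, treats death as non-informative censoring, and one minus the estimate overstates the probability of mastectomy. Because the rule is stated, it is not a detail left to a statistical analysis plan.

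Its size at 3 years is about 0.2 to 0.6 points for an assumed 3% mastectomy and 2% to 5% mortality per year, about 1.2 points at 60% 5-year survival, and 0.2 to 1.7 points over the wider grid. All of this rests on constant hazards and on mastectomy rates that the protocol does not supply.

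Severity is minor. MFI is secondary and descriptive, and neither the primary fibrosis conclusion nor the sample size is touched.

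**What to change.** In section 14.3, take MFI out of the Kaplan-Meier list. State that the probability of mastectomy will be estimated by the cumulative incidence function with death as a competing event, with 95% confidence intervals at 12 months, 24 months and 3 years. In section 10, replace the instruction to ignore all other events with one that treats death without mastectomy as a competing event and censors only patients alive without mastectomy at last follow-up.

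Leave L-RFS as defined. As an optional supplement, report beside it the cumulative incidence of second ipsilateral recurrence with death as a competing event, so that readers can separate relapse from death.

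Dates of mastectomy, recurrence and death are already needed for the planned endpoints. The cost is a few lines of text and one or two standard estimates, with no new visits, data items or patients.
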